10.5. Appendix 5: Abbreviations

Term	Definition
AE	adverse event
AITC	allyl isothiocyanate
blinding/masking	A double-blind study is one in which neither the participant nor any of the investigator or sponsor staff who are involved in the treatment or clinical evaluation of the subjects are aware of the treatment received.
CKD-EPI	Chronic Kidney Disease Epidemiology Collaboration
C_{max}	maximum serum/plasma concentration
complaint	A complaint is any written, electronic, or oral communication that alleges deficiencies related to the identity, quality, purity, durability, reliability, safety or effectiveness, or performance of a drug or drug delivery system.
compliance	Adherence to all study-related, good clinical practice, and applicable regulatory requirements.
CRF	case report form
CV%	percent coefficient of variation
CYP3A	cytochrome P450 enzymes 3A
DDI	drug-drug interaction
data monitoring committee	A data monitoring committee is a group of independent scientists who are appointed to monitor the safety and scientific integrity of a human research intervention, and to make recommendations to the sponsor regarding the stopping of a study for efficacy, or for harms, or for futility. The composition of the committee is dependent upon the scientific skills and knowledge required for monitoring the particular study.
DSA	disease-state addendum
ECG	electrocardiogram
eGFR	estimated glomerular filtration rate
enroll	The act of assigning a participant to a treatment. Participants who are enrolled in the study are those who have been assigned to a treatment.
IB	Investigator's Brochure
IC₅₀	half-maximal inhibitory concentration
IMP	Investigational Medicinal Product

informed consent	A process by which a participant voluntarily confirms his or her willingness to participate in a particular study, after having been informed of all aspects of the study that are relevant to the participant's decision to participate. Informed consent is documented by means of a written, signed, and dated informed consent form.
interim analysis	An interim analysis is an analysis of clinical study data, separated into treatment groups, that is conducted before the final reporting database is created/locked.
investigational product	A pharmaceutical form of an active ingredient or placebo being tested or used as a reference in a clinical trial, including products already on the market when used or assembled (formulated or packaged) in a way different from the authorized form, or marketed products used for an unauthorized indication, or marketed products used to gain further information about the authorized form.
ISA	intervention-specific appendix
NIMP	noninvestigational medicinal product
NOAEL	no observed adverse effect level
NRS	Numeric Rating Scale
OA	osteoarthritis
participant	Equivalent to CDISC term "subject": an individual who participates in a clinical trial, either as recipient of an investigational medicinal product or as a control
PK	pharmacokinetics
PO	by mouth
PoC	proof-of-concept
OA	osteoarthritis
QD	once daily
QTc	corrected QT interval
SAD	single ascending dose
SAE	serious adverse event
SAP	statistical analysis plan
screen	The act of determining if an individual meets minimum requirements to become part of a pool of potential candidates for participation in a clinical study.
SoA	Schedule of Activities
t_{1/2}	elimination half-life

TEAE	Treatment-emergent adverse event: An untoward medical occurrence that emerges during a defined treatment period, having been absent pretreatment, or worsens relative to the pretreatment state, and does not necessarily have to have a causal relationship with this treatment.
t_{max}	time to maximum plasma concentration
TRP	transient receptor potential
TRPA1	transient receptor potential ankyrin 1
WOCBP	women of childbearing potential

11. References

6.10.3. Secondary Efficacy Analyses.....	10
6.10.3.1. Key Secondary Analysis	11
6.10.3.2. Other Secondary Analysis	11
6.11. Bioanalytical and Pharmacokinetic/Pharmacodynamic Methods	11
6.12. Safety Analyses	12
6.12.1. Extent of Exposure.....	12
6.12.2. Adverse Events	12
6.12.3. Deaths, Other Serious Adverse Events, and Other Adverse Events for Review	13
6.12.4. Clinical Laboratory Evaluation	13

6.12.5. Vital Signs and Other Physical Findings	14
6.12.6. Electrocardiograms	14
6.12.7. Suicidal Ideation or Behavior	14
6.13. Subgroup Analyses	14
6.14. Protocol Deviations	15
6.15. Interim Analyses and Data Monitoring	15
6.16. Planned Exploratory Analyses	15
6.17. Totality of Evidence for Safety	15
6.18. Annual Report Analyses	16
6.19. Clinical Trial Registry Analyses	17
7. Unblinding Plan	18
7.1. PKPD Analysis Planning	18
8. References	19

3. Revision History

Statistical Analysis Plan (SAP) Version 1 was approved on 16 December 2021 prior to unblinding data for H0P-MC-OA02 (OA02).

SAP Version 2 was approved prior to unblinding data for Proof of Concept (PoC) lock. Major revisions included:

Section 5.2, assumptions for Average Pain Intensity as measured by the Numeric Rating Scale (API-NRS) power calculations were added.

Section 6.1, the language describing active-treatment and post active-treatment periods was made clearer.

Section 6.8, language was added to describe handling of specific edge cases when calculating treatment compliance.

Section 6.9, language describing reporting electronic Clinical Outcomes Assessment (eCOA) compliance separately for the active-treatment period was removed, since eCOA compliance is already reported on a weekly basis.

Section 6.10.1, language describing the derivation of nominal weeks for deriving the primary outcome was updated to handle a specific edge case observed in the BP03 readout.

Section 6.12.7, a section on suicidal ideation and behavior was added to include language that it would be reported separately for the active-treatment period.

Section 6.17, clarified the definition ,” , , , added a new endpoint under the Liver Function domain called DILI (drug-induced liver injury).

Section 7, added language that a CPMP-level blinding and unblinding plan now exists.

4. Study Objectives

4.1. Primary Objective

The primary objective of this intervention-specific appendix (ISA) is stated in the H0P-MC-CPMP (a) protocol. Additional blinded details regarding LY3526318 dosing that are not included in the protocol can be found in the Ethics Review Board (ERB) supplement for Study OA02. For Study OA02, endpoint is defined as 4 weeks post initial treatment administration at Visit 5. Unless otherwise specified, the time point for secondary endpoint measurements is the same as that for the primary endpoint.

Objectives	Endpoint
Primary	
Efficacy of LY3526318 versus placebo for pain intensity	Mean change from baseline assessment to 4 weeks for average pain intensity as measured by the NRS

Abbreviation: NRS = Numeric Rating Scale.

4.2. Secondary Objectives

Secondary objectives applicable to all ISAs are listed in the H0P-MC-CPMP (CPMP) SAP Version 5.

The key secondary objective for Study OA02 is to evaluate whether LY3526318 is superior to placebo in reducing pain as measured by the mean change from baseline assessment to Week 4 for pain intensity measured by the Western Ontario and McMaster University Arthritis Index (WOMAC®) pain subscale.

Additional secondary endpoints specific to Study OA02 are listed below.

Objective	Endpoint Measure
Other Secondary	
Efficacy of LY3526318 versus placebo for overall improvement	Mean change from baseline assessment to 4 weeks for overall improvements as measured by the Patient Global Impression of Change
Efficacy of LY3526318 versus placebo	Mean change from baseline to endpoint on the WOMAC® stiffness and physical function subscale Proportion of participants with reduction from baseline greater than or equal to 30%, 50%, and 70% on the WOMAC® pain subscale at each time point Proportion of participants with reduction from baseline greater than or equal to 30%, 50%, and 70% on the WOMAC® physical function subscale at each time point

Abbreviation: WOMAC = Western Ontario and McMaster University Arthritis Index.

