6.10.3. Secondary Efficacy Analyses

Secondary efficacy analyses common to all ISAs within CPMP have been described in the CPMP SAP Version 5. Unless otherwise specified, the time point for secondary endpoint measurements is the same as that for the primary endpoint. Study OA02 will also consider the following secondary analyses.

The Western Ontario and McMaster Universities Osteoarthritis Index (Bellamy 2005) is a validated instrument that is extensively used to evaluate the response to medications for the treatment of osteoarthritic pain. The WOMAC® version LK3.1 will be administered according to the Schedule of Activities.

This 24-question WOMAC® and its subscales are described as follows.

Dimensions/Subscales	Number of Questions
pain	5
stiffness	2
physical function	17

The participants will record their responses using a 0 to 4 Likert scale for each question:

0 = no pain (or stiffness or difficulty), and

4 = extreme pain (or stiffness or difficulty).

The scores for each subscale will be calculated by summing the scores of the questions in the respective subscale for each participant at each time point.

The range of possible scores for each subscale is pain = 0 to 20, stiffness = 0 to 8, and physical function = 0 to 68.

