6.10.3.1. Key Secondary Analysis

A Bayesian longitudinal mixed-model repeated measures analysis (MMRM) will be performed to evaluate the change from baseline to each postbaseline visit for the WOMAC® pain subscale, physical function subscale, and stiffness subscale. The model will utilize the constrained cell means model so that a common mean is estimated at baseline. More details on this approach are provided in the CPMP SAP Version 5.

Information included in the model is described as follows.

Categorical factors	the interaction of treatment and time point (constrained to estimate a common mean at baseline across treatments) average baseline pain severity category (baseline NRS < 7, baseline NRS ≥ 7) pooled investigative site
Continuous covariates	none

Abbreviation: NRS = Numeric Rating Scale.

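### Does describing the PGIC endpoint as a mean change from baseline leave it impossible to compute?

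*SAP*

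**What the plan says.** SAP Section 4.2 introduces its table of other secondary endpoints with "Additional secondary endpoints specific to Study OA02 are listed below". The first row serves the objective "Efficacy of LY3526318 versus placebo for overall improvement" and gives the endpoint as "Mean change from baseline assessment to 4 weeks for overall improvements as measured by the Patient Global Impression of Change". This is the sentence pattern that SAP Section 4.1 uses for the primary endpoint: "Mean change from baseline assessment to 4 weeks for average pain intensity as measured by the NRS". Section 4.1 also fixes the time point: "For Study OA02, endpoint is defined as 4 weeks post initial treatment administration at Visit 5".

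On analysis, SAP Section 6.10.3 says "Secondary efficacy analyses common to all ISAs within CPMP have been described in the CPMP SAP Version 5". Section 6.10.3.1 then sets out a Bayesian repeated-measures model to "evaluate the change from baseline to each postbaseline visit for the WOMAC® pain subscale, physical function subscale, and stiffness subscale", with the treatment-by-time term "constrained to estimate a common mean at baseline across treatments". Section 6.10.3.2 covers responder and time-to-response analyses of WOMAC thresholds. None of these OA02 sections names PGIC.

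The protocol supplied is an intervention-specific appendix. Its Section 9.3.1 places secondary endpoints and their analyses in the CPMP Master Protocol and the osteoarthritis disease-state addendum. Its Section 1.3 schedule covers only procedures unique to the appendix and refers the reader to those two documents for the rest.

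**The concern.** Average pain on the NRS is a state measured before and after treatment, so a change from baseline is natural. A global impression of change is different: before treatment there is no change to rate. Using the NRS wording for PGIC appears to require a baseline that has no meaning. The one secondary change-from-baseline model written out in this SAP estimates a baseline mean, which seems to make matters worse. The table also labels PGIC as specific to OA02, while Section 6.10.3 refers only analyses common to all appendices to the CPMP SAP, so it is unclear which text governs.

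If the row were programmed literally, two results might be feared. With no pre-dose rating, every participant would have a missing change score and the overall-improvement objective would have no result. With a pre-dose rating, subtracting it could add noise and blur the comparison of the arms.

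**Working it through.** The documents state no figure for this endpoint, so there is nothing to reproduce. The check has three parts.

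**1. Can the row be read so that it is computable?** The row asks for overall improvement as measured by PGIC, from baseline to 4 weeks. If the instrument rates change, the Week 4 rating is the measured change over that interval, and its mean in each arm is the endpoint. No pre-dose value is needed. The literal alternative, subtracting a pre-dose rating, needs a value that neither supplied document defines or schedules.

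**2. Does the SAP put PGIC through a model that needs a baseline?** Section 6.10.3.1 names three outcomes: WOMAC pain, physical function and stiffness. PGIC is not among them, and Section 6.10.3.2 is also limited to WOMAC. The baseline requirement therefore belongs to WOMAC, which has a baseline.

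**3. What would be lost under each way of programming it?** Let σ² be the variance of the Week 4 rating, σ_b² the variance of any pre-dose rating and ρ their correlation. The documents give none of these, so the values below are assumptions.

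*Week 4 rating by arm.* Variance per participant is σ². This is the reference, with SE ratio 1.

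*Constrained-baseline model, if borrowed for PGIC.* With common baseline mean μ₀ and Week 4 means μ_A and μ_P, the arm difference in change is

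(μ_A − μ₀) − (μ_P − μ₀) = μ_A − μ_P.

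The baseline mean cancels. At ρ = 0 the baseline carries no information on Week 4, so the SE ratio is about 1 (0% inflation). Baseline is one of the repeated outcomes, so a participant without a baseline rating still contributes post-baseline values. Complete loss of the endpoint does not follow.

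*Raw subtraction of a constant no-change value.* Here σ_b² = 0, so Var(post − constant) = σ² and the SE ratio is 1. The arm difference is unchanged.

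*Raw subtraction of a recorded pre-dose rating.* Var(post − base) = σ² + σ_b² − 2ρσσ_b. With σ_b = σ this is 2σ²(1 − ρ), and the SE ratio is √[2(1 − ρ)]:

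- ρ = 0: √2 = 1.41, a 41% increase.
- ρ = 0.5: √1 = 1, no increase.

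Only this last route can cost precision. It needs a pre-dose PGIC to be collected, to vary between participants, and to be subtracted outside the kind of model that the SAP describes. Neither supplied document plans that.

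**The case for a change.** The strongest case for acting is that PGIC is the only row of the Section 4.2 table without a method in this SAP. The WOMAC rows have a model in 6.10.3.1 or 6.10.3.2, and Section 6.10.3 gives WOMAC item counts, scoring and ranges. For PGIC there is no scale, direction or reference period. Because the table calls the endpoint specific to OA02, the referral of common analyses to the CPMP SAP may not reach it. The reference period also matters in this design. SAP Section 5.1 switches the active arm to placebo at Visit 5 and Section 6.1 calls for efficacy analyses over 8 weeks as well as 4, so a Week 8 rating means one thing if it refers back to the start of treatment and another if it refers to the previous visit.

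Much of this stands as a comment on drafting. The phrase is borrowed, and a pointer to the governing text would help a reader. It does not show a defect in the plan. Protocol Section 9.3.1 sends secondary endpoints and analyses to the master protocol and the addendum without limiting this to common ones, so the absence of a PGIC method here does not show that none exists. The reference period is a property of the instrument, which those documents may state. The row itself concerns Week 4, before any effect of the switch.

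**Conclusion.** The concern does not call for a change. The row carries a clerical slip: wording made for a pain scale was applied to a rating of change. The remaining gap is scale, schedule and model, which the documents cited by the protocol and SAP may supply and which analysts would fill in the same way, by summarising the Week 4 rating by arm. On that reading, with a constant subtracted, or under the constrained-baseline model at zero correlation, the precision of the arm contrast is essentially unaffected. The 41% figure holds only for raw subtraction of a recorded pre-dose rating with equal variances and zero correlation.

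The reach is small in any case. This is an other secondary endpoint in a proof-of-concept study with no formal multiplicity adjustment (SAP Section 6.4), and no sample size, power or false-positive figure rests on it. The conclusion assumes that the CPMP Master Protocol, the disease-state addendum and CPMP SAP Version 5, none of which was available, do not direct that a pre-dose PGIC rating be collected and subtracted.

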4.3. Exploratory Objectives

The following exploratory objectives and endpoints are specific to Study OA02.

Objectives	Endpoints
Tertiary/Exploratory	
Characterization of the pharmacokinetics of LY3526318 in participants with OA	Assessment of plasma concentrations of LY3526318 to enable pharmacokinetic evaluations
(Duration of response) Efficacy of LY3526318 versus placebo	Mean change from baseline assessment up to 8 weeks for average pain intensity as measured by the NRS

Abbreviations: NRS = Numeric Rating Scale; OA = osteoarthritis.

5. Study Design

5.1. Summary of Study Design

The CPMP protocol provides a summary of the overall study design for the chronic pain master protocol. ISA-specific study design is provided in the OA02 protocol.

In this ISA, patients in the LY3526318 treatment arm receive LY3526318 for the first 4 weeks of the double-blind period (active-treatment period) and switch to placebo for the last 4 weeks of the double-blind period (post-active-treatment period) starting on the day of Visit 5. Placebo patients receive placebo for the entire 8-week, double-blind period. Additional details of the study design may be found in the ERB supplement for Study OA02.

For the analyses listed in this SAP, except for treatment compliance, we define active-treatment period and post-active treatment period as follows. The first 4 weeks of the double-blind period (active-treatment period) ends at the day of Visit 5. The last 4 weeks of the double-blind period (post-active-treatment period) begins the day after Visit 5.

5.2. Determination of Sample Size

Approximately 150 participants will be randomized in a **CCI** ratio to LY3526318 and placebo. It is expected that approximately 85% or 128 participants will complete the double-blind treatment period of the study. **CCI**

CCI

If there is no treatment difference between placebo and LY3526318, the probability of passing the efficacy criterion specified above (that is, false positive) is less than 0.1. The simulation for the power calculation and sample size determination was carried out using the Fixed and Adaptive Clinical Trial Simulator (FACTS) Version 6.0.

CCI

If there is no treatment difference between placebo and LY3526318, the probability of passing the efficacy criterion specified above for average pain intensity (that is, false positive) is approximately 0.1.

5.3. Method of Assignment to Treatment

The method of treatment assignment is described in the CPMP SAP Version 5.

6. A Priori Statistical Methods

6.1. General Considerations

The estimand for the primary clinical question of interest has been described in the CPMP SAP Version 5.

The key secondary clinical question of interest is: What is the treatment difference between LY3526318 and placebo assessed using mean change from baseline to Week 4 for pain as measured by the WOMAC® pain subscale in participants with osteoarthritis of the knee regardless of initiation of rescue medication or other allowed concomitant medication and assuming that they would have continued initially randomized treatment condition?

Treatment condition: the randomized treatment along with potential use of rescue medication or other allowed concomitant medications regardless of adherence.

Population: participants with chronic pain conditions.

Endpoint: change from baseline to Week 4 in the WOMAC® pain subscale.

Intercurrent events: the intercurrent event is treatment discontinuation for any reason.

Population-level summary: difference in mean changes from baseline between treatment conditions.

The estimand is following a hypothetical strategy where efficacy of LY3526318 is assessed under the assumption that the participants would have continued their initially randomized treatment condition even if they discontinued.

Unless otherwise specified, efficacy analyses will be conducted for the first 4 weeks of the double-blind period (active-treatment phase) and separately for the entire 8-week study. A post active-treatment population will be used for analyses of the last 4 weeks of the double-blind period (post active-treatment phase) and will include all patients who do not discontinue at or prior to Visit 5. For treatment-emergent adverse events (TEAEs), participants in the post active-treatment population will be analyzed according to the treatment they receive during the active-treatment phase. Adverse event (AE) analyses will be reported for the first 4 weeks of the double-blind period (active-treatment phase) and separately for the last 4 weeks of the double-blind period (post active-treatment phase). Some AEs may be reported for the entire 8 weeks if necessary. Laboratory, electrocardiogram, and vital sign results will be reported for the active-treatment phase and separately for the entire 8-week study.

Other general considerations for analyses are described in the CPMP SAP Version 5.

6.2. Adjustments for Covariates

The general adjustment strategy has been described in the CPMP SAP Version 5.

6.3. Handling of Dropouts or Missing Data

The missing data strategy has been described in the CPMP SAP Version 5.

6.4. Multiple Comparisons/Multiplicity

There is no plan to formally adjust for multiplicity.

6.5. P P P P P /Subjects

There are no plans to use a modified efficacy subset.

6.6. Patient/Subject Disposition

The summary of patient disposition has been described in the CPMP SAP Version 5. Disposition will additionally be reported for the first 4-week, active-treatment period.

6.7. Participant Characteristics

The summary of participant characteristics has been described in the CPMP SAP Version 5.

6.8. Treatment Compliance

Treatment percentage of compliance will be calculated as:

$$\frac{\text{Total pills taken} * 100}{\text{Total pills expected}} \%$$

with total pills taken calculated by total pills dispensed minus total pills returned. A patient is considered to be compliant for a given period if this percentage is between 80% and 120%.

Treatment compliance will be reported for the first 4 weeks of the study period (Visit 3 to 5, not including the day of Visit 5) and separately for the last 4 weeks of the study period (Visit 5 to 7, including the day of Visit 5). Note that if a patient misses returning pills at Visit 4 or Visit 5, there will be an issue calculating compliance for the active treatment period and alternate methods for calculating compliance may be considered. For patients who discontinue early, time after the penultimate visit will be excluded for calculation of treatment compliance. For example, if a patient discontinued early at Visit 6, treatment compliance will be derived only from data collected through Visit 5. Comparisons between treatment group for treatment compliance will be performed using Fisher exact test. Listings for treatment compliance of individual patients by treatment period will also be provided.

Depending on the level of observed treatment compliance, and where appropriate, sensitivity analyses of primary or key secondaries may be conducted by excluding patients with poor treatment compliance.

